6.6.5.2. Other laboratory parameters

All other parameters collected on the eCRF will be listed in dedicated listings presenting all corresponding collected information on the eCRF.

- Coagulation: activated partial thromboplastin time (aPTT) and prothrombin time (INR).
- Urinalysis: all urinalysis parameters
- Other parameters: hormone, and immunology parameters
- Pregnancy test

The listings of laboratory results will be provided for all laboratory parameters. The listings will be sorted by parameters and assessment dates or visits for each patient. Laboratory values that are outside the normal range will also be flagged in the data listings, along with corresponding normal ranges. A listing of CTCAE grading will also be generated for those laboratory tests.

In addition, listings of abnormal values will be provided for hematology, chemistry, urinalysis, coagulation parameters. If there is at least one abnormal assessment for any parameter, all the data for that laboratory parameter will be included into the listing.

For all tests not mentioned above but present in the clinical data, a listing of patients with at least one result for the relevant test will be provided.

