13. **Contraception Check:** Patients who are of childbearing potential will need to affirm that they meet the criteria for correct use of 2 of the selected methods of contraception. The investigator or his or her designee will discuss with the patient the need to use 2 highly effective contraception methods consistently and correctly and document such conversation in the patient's chart. In addition, the investigator or his or her designee will instruct the patient to call immediately if one or both selected contraception methods are discontinued, or if pregnancy is known or suspected in the patient.
14. **Hematology:** No need to repeat on C1D1 if screening assessment performed within 7 days prior to that date. Required tests are listed in [Table 12](#) and will be performed every 2 weeks and the results should be available for review prior to infusion of treatment.
15. **Blood Chemistry:** No need to repeat on C1D1 if screening assessment performed within 7 days prior to that date. Full chemistry panel (required tests are listed in [Table 12](#)) is required at screening and Day 1 of each cycle and at End of Treatment/Withdrawal. Core chemistry panel (required tests are listed in [Table 12](#)) is required on Days 1 and 15 of each cycle. If full and core chemistry panels are scheduled at the same visit, only the full chemistry will be performed. **The results should be available for review prior to infusion of study treatment.**
16. **Coagulation:** No need to repeat on C1D1 if baseline assessment performed within 7 days prior to that date. Required tests are listed in [Table 12](#).
17. **ACTH and Thyroid Function Tests:** ACTH, Free T4 and TSH will be measured prior to trial treatment, every 8 weeks for 2 additional measurements, then every 12 weeks thereafter while on treatment, End of Treatment, at the 30-, 60-, 90-day post-treatment visits, and as clinically indicated.
18. **HBV serology, and HCV serology:** measured prior to study enrollment and then as clinically indicated.

19. **CA-125:** Will be assessed locally according to the schedule in the table.
20. **BRCA status.** If BRCA1/2 mutation status is known or becomes known for a patient during the study, this information will be recorded in the CRF either at screening or at later visits. No BRCA1/2 testing is required for this study.
21. **Urinalysis:** Dipstick is acceptable. Microscopic analyses must be performed if dipstick is abnormal.

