9.5. Safety Analysis

The Safety Analysis Set will be the primary population for safety evaluation. Summaries of AEs and other safety parameters will be provided by treatment arm as appropriate.

Adverse Events

Adverse events will be classified using the medical dictionary for regulatory activities (MedDRA) classification system. The severity of the toxicities will be graded according to the NCI CTCAE v4.03 whenever possible (<http://ctep.info.nih.gov/reporting/ctc.html>).

The frequency of patients experiencing treatment emergent adverse events corresponding to body systems and MedDRA preferred term will be reported. Adverse events will be graded by worst NCI CTCAE v4.03 Grade. Adverse events will be summarized by cycle and by relatedness to trial treatment.

Emphasis in the analysis will be placed on AEs classified as treatment emergent. Adverse events leading to death or discontinuation of trial treatment, events classified as NCI CTCAE v4.03 Grade 3 or higher, trial drug-related events, and serious adverse events will be considered with special attention. As appropriate, the difference in risk between treatment arms for AEs of clinical interest may be further assessed as described in the SAP.

Detailed information collected for each AE will include a description of the event, duration, whether the AE was serious, intensity, relationship to study treatment, action taken, and clinical outcome.

Laboratory Abnormalities

The laboratory results will be graded according to the NCI CTCAE v4.03 severity grade. The frequency of patients with laboratory test abnormalities will be summarized according to the worst grade for each laboratory test.

For laboratory tests without an NCI CTCAE grade definition results will be categorized as normal (within normal ranges), abnormal, or not done.

Shift tables will be provided to examine the distribution of laboratory abnormalities.

Electrocardiograms

ECG measurements (an average of the triplicate measurements) will be used for the statistical analysis and all data presentations. Single ECGs and data obtained from ECGs repeated for safety reasons after the nominal time-points will not be averaged along with the preceding triplicates. Interval measurements from repeated ECGs will be included in the outlier analysis (categorical analysis) as individual values obtained at unscheduled time points.

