- peak serum ALT(/ULN) vs peak total bilirubin (/ULN) including reference lines at ALT=3 \times ULN and total bilirubin=2 \times ULN.
- peak serum AST(/ULN) vs peak total bilirubin (/ULN) including reference lines at AST=3 \times ULN and total bilirubin=2 \times ULN.

In addition, a listing of all TBILI, ALT, AST and ALP values for patients with a post-baseline TBILI $\geq 2 \times \text{ULN}$, ALT $\geq 3 \times \text{ULN}$ or AST $\geq 3 \times \text{ULN}$ will be provided.

Parameters with NCI-CTC grades available:

The laboratory toxicities will be tabulated using descriptive statistics (number of patients and percentages) during the on-treatment period. The denominator to calculate percentages for each laboratory parameter is the number of patients evaluable for CTCAE grading (ie those patients for whom a Grade 0, 1, 2, 3 or 4 can be derived).

- The summary of laboratory parameters by CTCAE grade table will include number and percentage of patients with Grade 1, 2, 3, 4, Grade 3/4 and any grade (Grades 1-4), laboratory abnormalities during the on-treatment period.
- The shift table will summarize baseline CTCAE grade versus the worst on-treatment CTCAE grade. The highest CTCAE grade during the on-treatment period is considered as the worst grade for the summary.

The above analyses apply to hematology and chemistry evaluations which can be graded per CTCAE, ie:

- Hematology:

Hemoglobin (HB), Leukocytes (white blood cell decreased), Lymphocytes (lymphocyte count increased/decreased), Neutrophils / Absolute Neutrophils Count (ANC) (neutrophil count decreased), Platelet Count (PLT) (platelet count decreased).

- Serum Chemistry:

Albumin (hypoalbuminemia), Alkaline Phosphatase (alkaline phosphatase increased), Alanine Aminotransferase (ALT) (ALT increased), Amylase (serum amylase increased), Aspartate Aminotransferase (AST) (AST increased), Total Bilirubin (blood bilirubin increased), Cholesterol (cholesterol high), Creatinine (creatinine increased), Creatine Kinase (CPK increased), Potassium (hypokalemia/ hyperkalemia), Sodium (hyponatremia/ hypernatremia), Magnesium (hypomagnesemia/hpermagnesemia), Calcium (hypocalcemia/ hypercalcemia), Glucose (hypoglycemia/hyperglycemia), Gamma Glutamyl Transferase (GGT) (GGT increased), Lipase (lipase increased), Phosphates (hypophosphatemia), Triglycerides (hypertriglyceridemia).

Parameters with NCI-CTC grades not available:

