Hematology and chemistry evaluations which cannot be graded per CTCAE criteria will be summarized as frequency (number and percentage) of patients with:

- shifts from baseline normal to at least one result above normal during on-treatment period
- shifts from baseline normal to at least one result below normal during on-treatment period

In this study, these apply to the following parameters:

- Hematology: Absolute Monocytes, Absolute Eosinophils, Absolute Basophils
- Serum Chemistry: Chloride, Total Urea, Uric Acid, Total Protein, C-Reactive Protein, Lactate Dehydrogenase (LDH)

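### Scheduled TSH and free T4 results go to listings only, so out-of-range thyroid values are never counted by arm (minor, descriptive)

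*SAP*

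**What the plan says.** **Collection.** Footnote 17 of the protocol's original Schedule of Activities states that "ACTH, Free T4 and TSH will be measured prior to trial treatment, every 8 weeks for 2 additional measurements". Testing then continues every 12 weeks on treatment, at end of treatment, and at the day 30, 60 and 90 visits. The row has no arm restriction, so the PLD-alone arm is tested on the same schedule.

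**Protocol analysis plan.** Protocol 9.5 says: "For laboratory tests without an NCI CTCAE grade definition results will be categorized as normal (within normal ranges), abnormal, or not done". It adds: "Shift tables will be provided to examine the distribution of laboratory abnormalities".

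**SAP analysis plan.** SAP 6.6.5.1 is headed as covering hematology and chemistry. For the grade and shift tables it says "The above analyses apply to hematology and chemistry evaluations which can be graded per CTCAE" and then names them. A second named list covers ungraded tests, which are summarized as shifts from a normal baseline to at least one high or at least one low value. SAP 6.6.5.2 deals with the rest: "All other parameters collected on the eCRF will be listed in dedicated listings presenting all corresponding collected information on the eCRF". One bullet under that rule reads "Other parameters: hormone, and immunology parameters". The section then says: "In addition, listings of abnormal values will be provided for hematology, chemistry, urinalysis, coagulation parameters". Hormones are not in that last sentence.

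**The concern.** Thyroid dysfunction is a known avelumab toxicity. Protocol 1.2.2.4 reports hypothyroidism as an immune-related event in 5 of 75 ovarian cancer patients (6.7%), the most frequent of the immune-related events it names. That is an adverse event count and does not measure the gap described here, but it shows why these two tests matter.

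The trial is open-label. Adverse event reports, immune-related classification and hormone replacement all depend on someone who knows the assigned arm deciding to report or treat. Scheduled laboratory values depend on such decisions much less. A by-arm count of out-of-range results is therefore a useful check beside the event tables, and PLD alone provides a concurrent comparator. The SAP tabulates shifts for chloride, uric acid and total protein, but not for the tests that detect this toxicity.

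**Working it through.** No formula applies. The check is which parameters are tabulated and which are only listed.

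**1. Parameters named for tables in SAP 6.6.5.1**

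| List | Hematology | Chemistry | Total | TSH or free T4 |
|---|---|---|---|---|
| CTCAE-graded | 5 | 18 | 23 | 0 |
| Ungraded (shift from normal) | 3 | 6 | 9 | 0 |
| Both | 8 | 24 | 32 | 0 |

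**2. Whether the thyroid tests could count as chemistry.** Protocol Table 12 gives them their own Thyroid Function Tests row, outside Chemistry. The SAP's laboratory section does not name TSH or free T4, so placing them under hormones is an inference. It is a safe one, because no other SAP laboratory class fits.

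**3. What remains for hormones in SAP 6.6.5.2.** They get the full listing, with out-of-range values flagged and normal ranges shown. They are not in the separate listings of abnormal values, which cover hematology, chemistry, urinalysis and coagulation.

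**4. By-arm outputs that touch on thyroid function**

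| Output | What it counts |
|---|---|
| TEAEs by preferred term and worst grade (SAP 6.6.1.1) | Events the investigator reported |
| Immune-related AEs with risk differences, CIs and p-values (SAP 6.6.4, Appendix 1) | Reported events, onset up to 90 days after last dose; the programmed definition requires that the event was treated; medical review may add cases |
| Concomitant medications (SAP 6.5.4) | Therapy given; therapy continued from before first dose is counted with new therapy |

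None of these counts laboratory values.

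**5. Post-treatment tests and the on-treatment window.** SAP 5.2.7 ends the window at last dose + 30 days, or the day before new anti-cancer drug therapy if that is earlier. The follow-up visits have a window of 3 days either way, and the final visit may not fall before day 90.

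- Day-30 test: 30 − 3 = 27 to 30 + 3 = 33. Days 27 to 30 fall inside the 30-day limit; days 31 to 33 fall outside.
- Day-60 test: earliest 60 − 3 = day 57, outside.
- Final test: days 90 to 93, outside.

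The window applies to all summarized safety data, so it is not a thyroid-specific fault. It matters here only for deciding what an added table would include.

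**The case against.** The strongest reply is that clinically important results already have a route into the tables. Protocol 8.5 makes an abnormal result an adverse event if it comes with symptoms, needs further testing or intervention, leads to a dosing change outside the protocol's rules, discontinuation or significant added treatment, or is judged an event by the investigator or sponsor. Protocol Table 6, in force until Amendment 2, also set a trigger: TSH below 0.5 × LLN, above 2 × ULN, or consistently out of range on 2 subsequent measurements. The response was T4 testing as clinically indicated and consideration of an endocrinology consult. Acting on that trigger can itself make the result reportable. What is left uncounted is then mainly values that prompted none of these responses. This reply stands as a limit on the importance of the point. It does not supply the missing count, because every step depends on a clinical action or judgement.

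A second reply is that SAP 6.6.5.1 has a general sentence promising low/normal/high categories for results outside CTCAE. That sentence sits under the hematology and chemistry heading, and the named lists narrow it. SAP 6.6.5.2 then says what happens to hormones.

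Third, SAP 6.5.4 also summarizes prior medications separately, so pre-dose thyroid therapy is visible. That helps. But the prior group also includes drugs stopped before first dose, so the two tables cannot simply be subtracted to give new thyroid therapy per arm.

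It is also true that the SAP may modify the protocol (SAP Section 2, Protocol Section 9), that SAP 3.5.1 treats safety analyses as generally exploratory, and that a reader with the listing could count the flagged rows. This is therefore a narrowing of the protocol's plan and not a breach of it.

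**Conclusion.** The point holds as a minor, descriptive gap. Of the 32 parameters named for the SAP 6.6.5.1 tables, none is a thyroid test, and SAP 6.6.5.2 leaves hormones in listings. There is no by-arm count of out-of-range TSH or free T4, although Protocol 9.5 described normal/abnormal categories for ungraded tests, and shift tables.

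The clinical size is unknown. The documents give no number of patients with a laboratory abnormality and no reported event, and none is assumed. No primary conclusion is affected, and the individual values remain visible. The conclusion rests on reading the thyroid tests as hormone parameters and on treating the named lists in SAP 6.6.5.1 as complete.

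**What to change.** Add TSH and free T4 to the SAP 6.6.5.1 table for parameters without CTCAE grades, and exempt them from the listings-only hormone bullet in SAP 6.6.5.2.

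- **Counts:** per arm, number and percentage of patients going from a normal baseline to at least one value above normal, and separately to at least one below.
- **Denominator:** patients with a normal baseline and at least one post-baseline value.
- **Window:** the existing on-treatment period in SAP 5.2.7.
- **Separate line:** patients with thyroid disease or thyroid medication at baseline (ATC H03A or H03B, the codes Appendix 1 already uses for endocrinopathies). Exclusion criterion 17 let patients with hypo- or hyperthyroid disease enter if they did not need immunosuppressive treatment.
- **Context:** the number of scheduled thyroid tests done per arm, shown beside the counts.
- **Optional row:** scheduled values through the day-90 visit (up to day 93), stopping the day before new anti-cancer drug therapy, since Protocol 5.4.6 prohibits no therapy in follow-up.

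The cost is a change of wording and two added parameters in an existing descriptive table, with no new samples or visits. Protocol Section 9 says the final analysis is complete, so in practice this would be a supplementary table. The drawback is that the counts depend on time on treatment, so they must be read with the number of tests per arm.

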6.6.6. Vital signs

Weight for the purposes of dose calculation will be recorded at screening and within 3 days pre-dose Day 1 of each cycle. Weight will not be collected at End of Treatment. Height will be measured at screening only.

Vital sign summaries will include all vital sign assessments from the on-treatment period. All vital sign assessments will be listed, and those collected outside the on-treatment period will be flagged in the listing.

All vital sign parameters will be summarized using descriptive statistics (mean, SD, median, Q1, Q3, minimum, and maximum) of actual values and changes from baseline for each visit over time. End of Treatment visit will be summarized separately. The changes computed will be the differences from baseline.

6.6.7. Electrocardiogram

ECG summaries will include all ECG assessments from the on-treatment period. All ECG assessments will be listed, and those collected outside the on-treatment period will be flagged in the listing. QTcB and QTcF will be derived based on RR and QT (see below). The average of the replicate measurements should be determined after the derivation of the individual parameter at each time point.

Selecting Primary QT Correction for Heart Rate

The analysis of QT data is complicated by the fact that the QT interval is highly correlated with heart rate. Because of this correlation, formulas are routinely used to obtain a corrected value, denoted QTc, which is independent of heart rate. This QTc interval is intended to represent the QT interval at a standardized heart rate. Several correction formulas have been proposed in the literature. For this analysis we will use some of those methods of correction, as described below. The QT interval corrected for heart rate by the Bazett's formula, QTcB, is defined as

$$QTcB = \frac{QT}{\sqrt{RR}},$$

the QT interval corrected for heart rate by the Fridericia's formula, QTcF, is defined as

$$QTcF = \frac{QT}{\sqrt[3]{RR}}$$

where RR represents the RR interval of the ECG, in seconds, and can be estimated as 60/Heart Rate.

Although Bazett's correction is the historical standard, it does not perform well when heart rate fluctuates. Fridericia's formula may perform better under these conditions. If QTcB and QTcF methods do not adequately correct for HR and there are a sufficient number of patients (eg >30) with baseline ECGs, an alternate correction to achieve the goal of getting uncorrelated QTc and RR is based on a linear regression methods which yields, theoretically, uncorrelated QTc and RR.

Linear regression method:

- Fit a model $QT = a + b \times RR$ to baseline data
- Use the estimated slope, \hat{b} , to correct QT
- Corrected QT for heart rate will be computed as follows:

$$QTcP = QT + \hat{b} \times (1 - RR)$$

Data will be summarized using QTcF and QTcB. However, if these are not appropriate for the data set due to an observed large correlation between corrected QT and HR using the baseline assessments, the results will also be summarized using QTcP.

ECG Summaries

The following analyses will be performed for each applicable ECG parameters (RR, PR, QRS, QT, ventricular rate -denoted as HR in what follows-, and QTc) by treatment arm, during the on-treatment period. The denominator to calculate percentages for each category is the number of patients evaluable for the category.

- Pearson correlation between QT and HR, QTc (QTcB, QTcF and, if applicable, QTcP) and HR using individual (non-averaged) baseline assessments
- For each of the ECG parameters (HR, and QT, QTc, QRS, PR intervals), descriptive statistics at baseline, at each post-baseline time point and changes from baseline at each post-baseline time point
- Frequency (number and percentage) of patients with notable ECG values according to the following categories:
 - QT/QTc increase from baseline >30 ms, >60 ms
 - QT/QTc > 450 ms, > 480 ms, > 500 ms

- HR \leq 50 bpm and decrease from baseline \geq 20 bpm
- HR \geq 120 bpm and increase from baseline \geq 20 bpm
- PR \geq 220 ms and increase from baseline \geq 20 ms
- QRS \geq 120 ms

Patients with notable ECG interval values and qualitative ECG abnormalities will be listed for each patient and time point and the corresponding notable values and abnormality findings will be included in the listings.

Unscheduled ECG measurements will not be used in computing the descriptive statistics for change from baseline at each post-baseline time point. However, they will be used in the analysis of notable ECG changes and the shift table analysis of notable QT parameters.

6.6.8. MUGA/ECHO

LVEF% will be summarized using simple descriptive statistics (mean, SD, median, Q1, Q3, minimum, and maximum) of actual values and changes from baseline for each nominal visit over time. In addition, LVEF% will be summarized as frequency (number and percentage) of patients with:

- a shift from baseline normal to at least one result below the institutional lower limit of normal (LLN) during the on-treatment period
- \geq 10-point decrease from baseline in LVEF% during the on-treatment period
- \geq 10-point decrease from baseline in LVEF% to a post-baseline value $<$ LLN during the on-treatment period
- \geq 15-point decrease from baseline in LVEF%
- \geq 15-point decrease from baseline in LVEF% to a post-baseline value $<$ LLN during the on-treatment period.

Clinically significant findings will be listed.

6.6.9. Physical examination

Number and percentage of patients with abnormal findings in physical examination will be summarized by body system.

6.6.10. ECOG performance status

The ECOG shift from baseline to highest score during the on-treatment period will be summarized by treatment arm. ECOG performance status with shift from ECOG=0 or 1 to ECOG 2 or higher will also be presented in a data listing.

7. INTERIM ANALYSES

7.1. Introduction

The goals of the interim analyses are to allow early stopping of treatment arm(s) for futility or declare an experimental treatment (or treatments) to be statistically significantly superior to the control treatment arm. The interim analysis of OS and PFS will be performed as described in Sections 5.1.1 and 5.1.2 using the methodology described in Section 6.1.1 for OS and Section 6.1.2 for PFS.

The interim analyses for PFS and OS will occur at the same time and will be performed by an independent statistician.

Unblinded results from the interim analysis for OS and PFS will not be communicated to the Sponsor's clinical team or to any party involved in the study conduct (apart from the independent statistician and E-DMC members) until the E-DMC has determined that either (i) OS or PFS analysis has crossed the pre-specified boundary for efficacy or (ii) the study needs to be terminated due to any cause, including futility or safety reasons. Further details will be described in the E-DMC charter.

At the time of the final PFS and OS analyses, both PFS and OS analysis will be performed by the Sponsor's clinical team.

